2.2.1 Subgroup of interest

In general no subgroups are displayed. In selected tables (see Tables/Listings/Figures-Shells) the data are displayed separately for the subcohorts 1a, 1b, 2a, and 2b.

2.3 Patient disposition, demographics and other baseline characteristics

Demographic and other baseline data including disease characteristics will be summarized descriptively by treatment group (ofatumumab before versus after vaccination) for the SAF and the Efficacy Analysis Set.

If major imbalance in relevant demographic or other baseline characteristics are discovered, the study results will be interpreted with more caution and post-hoc supportive analyses may be conducted to adjust for the imbalance.

2.3.1 Patient disposition

Patient disposition displays the absolute and relative frequency of screening failures, the number of patients included in the different analysis sets.

The reasons for screening failure, for missed study visits, for exclusion from analysis populations and for premature drop-out are described by frequency tables as well as protocol deviations.

The duration of intervals between relevant study visits are displayed by sample statistics.

2.4 Treatments (study treatment, rescue medication, concomitant therapies, compliance)

2.4.1 Study treatment / compliance

The absolute and relative frequency of performed study visits (restricted to visits which are relevant for efficacy analysis) and performed vaccinations are presented. Sample statistics for the duration of intervals between screening and 1st resp. booster vaccination, 1st and 2nd vaccination, 2nd resp. booster vaccination and Week 1/Month 1/Month 6/ Month 12 after Vaccination 2 resp. booster vaccination are displayed. Here always the exact date of the respective vaccination is used but not the date of study visit called “Vaccination 1” or “Vaccination 2” or “Booster Vaccination” which displays the date of phone contact with the patient.

Two types of investigational study drugs are used in this study:

1. Ofatumumab for treatment of MS
2. mRNA vaccine

The interval of ofatumumab start is displayed relatively to the 1st resp. booster vaccination for cohort 2, and relatively to the 2nd resp. booster vaccination for cohort 1. Sample statistics are provided for these intervals. The frequencies of patients with temporary interruption respectively permanent discontinuation until each efficacy assessment time point (Week 1, Month 1, 6, 12, and 18) are provided.

The different vaccines are displayed by a frequency table separately for 1st and 2nd vaccination.

2.4.2 Prior, concomitant and post therapies

The number and types of all pretreatments for multiple sclerosis prior to screening are displayed. Here, all MS-therapies except ofatumumab which are starting before screening and ongoing after screening are included into counts.

The last disease modifying drug before ofatumumab respectively the number of treatment-naïve patients is displayed in a frequency table.

Concomitant medications are coded by WHO Drug-dictionary. Frequencies of Anatomic Therapeutic Chemical (ATC) categories and Preferred Names are presented. Here, a medication with multiple entries is counted only once in a ATC category respectively a preferred name category.

2.5 Analysis of the primary objective

2.5.1 Primary endpoint

The **primary clinical question** of interest is: What is the proportion of RMS patients having developed a specific immune response after receiving a modRNA vaccine (either initial vaccination or booster) either before or after starting ofatumumab treatment. The justification for the primary estimand is that it will capture whether ofatumumab-treated patients will mount

a specific T-cell response after receiving a SARS-CoV-2 mRNA vaccine assessed by enzyme-linked immunosorbent spot (ELISpot) assays from T-cells that were stimulated with SARS-CoV-2 peptide mix. Patients will receive either their initial vaccination (1st and 2nd SARS-CoV-2 vaccines) or a booster vaccine before or after starting ofatumumab treatment. In both cases we want to assess if ofatumumab initiation negatively affects or prevents the immune response.

Since this is not a randomized trial, no randomization needs to be preserved and the ITT-principle and the associated estimands framework do not apply. However, this protocol will keep as close as appropriate to the terminology and the definitions established within that framework.

The primary estimand is described by the following attributes:

1. **Population:** Patients with relapsing MS (RMS) divided in two cohorts, each receiving a SARS-CoV-2 mRNA vaccine as part of clinical routine: (1) vaccination before start of ofatumumab treatment, (2) vaccination after having been on stable ofatumumab treatment for at least 4 weeks. The SARS-CoV-2 mRNA vaccine can be either the initial vaccination cycle (for patient that are exposed to the vaccine for the first time; cohort 1a and cohort 2a) or a booster vaccination (for patients that have already completed the initial vaccination cycle; cohort 1b and cohort 2b). Patients in cohort 1a or 2a who fail to receive their second dose of vaccine for whatever reason will be included in the analysis as non-responders. Patients in cohorts 1a and 2a who did receive their second dose of vaccine and patients in cohorts 1b and 2b who received their booster shot and do not have a valid determination of specific T-cell response to SARS-CoV-2 for whatever reason will be excluded from the analysis of vaccine efficacy.
2. **Variable:** Receiving the second dose of mRNA vaccine (for cohort 1a and 2a) or a booster vaccination (cohort 1b and 2b) and mounting a specific T cell response² one month after second dose of vaccine (cohort 1a and 2a) or booster vaccine (cohort 1b and 2b) defined by detection of SARS-CoV-2 specific T-cells by ELISpot assays after stimulation of T-cells with SARS-CoV-2 peptide mix (yes/no)
3. **Treatment of interest:** ofatumumab treatment, which is started either before or after receiving a SARS-CoV-2 mRNA vaccine (initial vaccination cycle or booster vaccine)
4. **Intercurrent events:**
 - a. Vaccination with a non-mRNA vaccine: patients will be excluded from the study
 - b. Failure to receive the second dose (for cohorts 1a and 2a) of vaccine: patients will be classified as non-responders
 - c. Failure to initiate ofatumumab treatment within six weeks after completion of the vaccination cycle (cohort 1a) or of the booster vaccine (cohort 1b): patients will be excluded from the efficacy analyses

² See appendix 5.3.1 for derivation

d. Failure to complete ofatumumab initiation or interruption of ofatumumab treatment prior to first vaccination (cohort 2a) or prior to booster vaccination (cohort 2b): patients will be excluded from the study

e. No valid detection of SARS-CoV-2 specific T-cells: patients will be excluded from the efficacy analyses if they received their second dose of vaccine (cohorts 1a and 2a) or booster vaccine (cohort 1b and 2b) and further analyses will be performed to confirm methodical reasons

5. **Summary measure:** n.a., there will be no formal comparison between cohorts. Response rates will only be calculated within each cohort.

2.5.2 Statistical hypothesis, model, and method of analysis

The efficacy analysis set is used for all analyses of the primary parameter.

The primary analysis will not use any statistical testing or modelling. The absolute numbers and the proportion of participants achieving SARS-CoV-2-specific T-cell response within each cohort will be calculated. It will be augmented by a (descriptive) two-sided 95% confidence interval (exact Clopper-Pearson).

2.5.3 Handling of missing values/censoring/discontinuations

Cohort 1a and cohort 2a: Patients who fail to receive their first dose of vaccine for whatever reason are excluded from the efficacy analysis Set(s). The number of these patients is displayed in the patient disposition table.

Patients who fail to receive their second dose of vaccine for whatever reason will be included in the analysis as non-responders. The number of these patients is displayed in the analysis table.

Patients who did receive their second dose of vaccine and do not have a valid determination of reactive T-cells to SARS-CoV-2 for whatever reason will be excluded from the analysis of vaccine efficacy at the respective time point. The number of these patients is displayed in the analysis table.

Cohort 1b and cohort 2b: Patients who fail to receive their booster vaccination for whatever reason are excluded from the efficacy analysis Sets(s). The number of these patients is displayed in the patient disposition table.

Patients who did receive their booster vaccination and do not have a valid determination of reactive T-cells to SARS-CoV-2 for whatever reason will be excluded from the analysis of vaccine efficacy at the respective time point. The number of these patients is displayed in the analysis table.

2.5.4 Supportive analyses

The reactivity towards SARS-CoV-2 and towards PAN coronaviridae is analysed by frequency tables presenting each investigational visit. This applies to the parameters:

- IFNg (qualitative, i.e. reactive, equivocal, not reactive)
- IL-2 (qualitative, i.e. reactive, equivocal, not reactive)

The stimulation index towards SARS-CoV-2 and towards PAN coronaviridae is analysed by sample statistics and a boxplot graph for each investigational visit. This applies to the parameters:

- IFNg (quantitative)
- IL-2 (quantitative)

If relevant differences in demographic or other baseline characteristics are observed post-hoc analysis will be performed to adjust the primary endpoint for these inhomogeneities. A logistic regression model would be applied.

2.6 Analysis of the key secondary objective

Not applicable, because no key secondary objectives are specified.

2.7 Analysis of secondary efficacy objective(s)

2.7.1 Secondary endpoints

The secondary endpoints are analyzed descriptively within each cohort. The Efficacy Analysis Set is used for all analyses of the secondary parameters.

The proportion of patients achieving seroconversion³ in SARS-CoV-2 neutralizing antibodies is presented for the time points Month 1, Month 6, and Month 12. Exact confidence intervals (95%, two-sided) are calculated by the Pearson-Clopper method.

The phenotypical parameters are displayed by sample statistics and boxplots per time point (Screening, Month 1, Month 6, and Month 12) by cohort. For the baseline visit the subcohorts are presented. This applies to these parameters:

- CD19+/CD20+ B cells (absolute and relative values)
- CD4+ cells (% of mononuclear cells)
- CD4: IL4 basal and stimulated, IFNg basal and stimulated (%)
- CD4 naïve: IL4 basal and stimulated, IFNg basal and stimulated (%)
- CD4 TCM: IL4 basal and stimulated, IFNg basal and stimulated (%)
- CD4 TEM CD27 – and CD27+: IL4 basal and stimulated, IFNg basal and stimulated (%)
- CD8+ cells (% of mononuclear cells)
- CD8: IL4 basal and stimulated, IFNg basal and stimulated (%)
- CD8 naïve: IL4 basal and stimulated, IFNg basal and stimulated (%)
- CD8 TCM: IL4 basal and stimulated, IFNg basal and stimulated (%)
- CD8 TEM CD27 – and CD27+: IL4 basal and stimulated, IFNg basal and stimulated (%)

³ For derivation of seroconversion see Appendix 5.3.2

All other laboratory data (e. g. number of basal/background spots, spots, quality, comments, mutations and hematology) are listed only.

The MS activity is measured by relapses. The crude annual relapse rate until end of study and the underlying sums (of relapses and patient-years) will be presented.

2.7.2 Statistical hypothesis, model, and method of analysis

Not applicable due to descriptive analysis.

2.7.3 Handling of missing values/censoring/discontinuations

Missing values are not replaced.

2.9 Safety analyses

All safety analyses are presented for the Safety Set (SAF). Descriptive statistics are presented within study treatment groups (cohorts 1 and 2).

2.9.1 Adverse events (AEs)

According to the CSP all adverse events starting in the on-treatment period, i. e. the treatment-emergent AEs, are analyzed.

The on-treatment period lasts from the date of first administration of study treatment⁴ after informed consent to 30 days after the last visit.

⁴ Study treatment is ofatumumab as well as the modRNA vaccine.

The number (and percentage) of subjects with treatment-emergent adverse events will be summarized in the following ways:

- by treatment group (cohort 1 and 2), primary system organ class and preferred term.
- by treatment group (cohort 1 and 2), primary system organ class, preferred term and maximum severity
- by type of modRNA (Biontech/Pfizer versus Moderna), primary system organ class and preferred term.

A subject with multiple AEs within a MedDRA primary system organ class is only counted once towards the total of the primary system organ class.

A subject with multiple AEs within a preferred term is only counted once towards the total of the preferred term class.

Separate summaries will be provided for study medication related AEs, death, SAEs, AEs leading to discontinuation and adverse events leading to dose adjustment.

The absolute and relative frequency of COVID-19 infections is presented.

Deaths and serious adverse events are listed in addition. Deaths outside the on-treatment period are listed in addition.

Rates of COVID-19 infections and the rate of COVID-19 infections starting ≥ 7 days after the 2nd vaccination are displayed. All COVID-19 infections are listed with the dates of all COVID-19 vaccinations.

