- For cohort 1a, screening and baseline can be performed on the same day, and have to be performed before the first vaccination. Possible effects of the previous MS treatment on vaccination efficacy should be kept in mind when scheduling SARS-CoV-2 vaccination. For cohort 1b, screening and baseline can be performed any time after completion of the initial vaccination cycle and should be approx. 1 week before the first SARS-CoV-2 booster vaccine. Possible effects of the previous MS treatment on booster vaccine efficacy should be kept in mind when scheduling SARS-CoV-2 booster vaccination.
- For cohort 2a and 2b, the run-in period includes initiation of ofatumumab treatment as per approved SmPC and lasts for at least 4 weeks after the first ofatumumab dosing. For cohort 2a and 2b, additional visits during the run-in period will be necessary: one visit to start ofatumumab treatment (can be performed at screening), three remote visits (e.g. phone calls) 1, 2 and 4 weeks after the first ofatumumab dose to ensure the application of the first ofatumumab doses according to SmPC, and the baseline visit approx. 1 week
 - before the first vaccine (cohort 2a).
 - before the first booster vaccination (cohort 2b)

Patients that have already been on stable ofatumumab treatment for at least 4 weeks before the screening visit will follow the run-in period assessment schedule for cohort 1: no additional visits except screening/baseline will be needed. Assessments during the study period will be performed as defined for cohort 2.

The **study period** starts for cohorts 1a and 2a with the first SARS-CoV-2 modRNA vaccination and ends 18 months after the second vaccination (EOS). All patients will return to the study site 1 week, 1 month, 3 months, 6 months, 12 months and 18 months after the second vaccination for study visits. During the study, patients are allowed to receive additional SARS-CoV-2 vaccines (as booster shot or yearly refresher) if suggested by local regulations and as per physician's discretion.

For cohorts 1b and 2b, the study period starts with the first booster vaccination and patients will return to the study site 1 month (equivalates 4 weeks), 3 months, 6 months and 12 months (EOS) after the booster vaccine.

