5.2 Treatment-emergent adverse events

Treatment emergent AEs are those which start in the on-treatment period. The on-treatment period lasts from the date of first administration of study medication after informed consent to 30 days after the last visit.

The date of first administration of study medication is the date of 1st vaccination or the date of first ofatumumab at or after screening whichever is earlier.

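### The adverse-event table by vaccine brand counts events over the whole on-treatment period, including time before any study vaccine dose, and the SAP has no rule for patients with more than one brand

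*SAP*

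**What the plan says.** SAP 2.9.1 takes as its scope "all adverse events starting in the on-treatment period, i. e. the treatment-emergent AEs, are analyzed". It then lists three breakdowns. Two are by cohort; the third is "by type of modRNA (Biontech/Pfizer versus Moderna), primary system organ class and preferred term". No separate event definition is given for the third.

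The on-treatment period runs from the first study treatment "after informed consent to 30 days after the last visit". A footnote in the same section says "Study treatment is ofatumumab as well as the modRNA vaccine", and SAP 5.2 fixes the start: it "is the date of 1st vaccination or the date of first ofatumumab at or after screening whichever is earlier".

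Protocol section 3 (Study design) says that for cohorts 1a and 2a the study period "ends 18 months after the second vaccination (EOS"; for 1b and 2b the last visit is 12 months after the booster.

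On the population, SAP 2.9 states: "All safety analyses are presented for the Safety Set (SAF". SAP 2.2 defines that set as everyone who received any study drug. SAP 5.4 lists deviation S02, different vaccines at doses 1 and 2, and removes those patients from the Efficacy Analysis Set only.

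On which vaccines were used, SAP 2.4.1 says: "The different vaccines are displayed by a frequency table separately for 1st and 2nd vaccination". Boosters are not mentioned there.

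**The concern.** A table of adverse events by vaccine brand is read as information about the vaccines. Here most of the counted time is far from any vaccine dose and, in part of cohort 2, some of it comes before vaccination.

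Brand is also a property of a dose, not necessarily of a patient. Patients in 1b and 2b completed an initial series before the study and receive a booster in it. Patients in 1a and 2a may receive boosters after dose 2, and 1b and 2b patients may receive further ones. No text requires these to match the earlier brand, and no text says which dose determines the column.

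Finally, the percentage of patients with an event grows with follow-up, which differs by about six months between the a and b subcohorts. If brand use also differs between them, the columns can differ for that reason alone.

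At stake is whether this one table can be interpreted. No objective or primary result depends on it.

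**Working it through.** The documents give no figure for this table, so there is nothing to reproduce. The check is how long the counted period is and how much of it lies near a dose.

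**Inputs**
- Follow-up: 18 months after dose 2 (1a/2a) or 12 months after the booster (1b/2b), protocol section 3. One month = 30.44 days, so 548 and 365 days.
- Tail: 30 days, SAP 2.9.1.
- Dose 1 to dose 2: 3 or 4 weeks, given as examples in protocol 4.5.
- Ofatumumab lead-in before vaccination, cohort 2: 4 to 12 weeks, protocol 4.5.
- For 1b, the period is taken to open at the study booster, because SAP 2.9.1 counts treatment only from informed consent.
- A 28-day window is my assumption, for illustration; the documents set none for adverse events.

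**Length of the period** = lead-in + dose interval + follow-up + 30

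| Subcohort | Sum (days) | Period (days) |
|---|---|---|
| 1a | (21 or 28) + 548 + 30 | 599 or 606 |
| 1b | 365 + 30 | 395 |
| 2a, shortest | 28 + 21 + 548 + 30 | 627 |
| 2a, longest | 84 + 28 + 548 + 30 | 690 |
| 2b, shortest | 28 + 365 + 30 | 423 |
| 2b, longest | 84 + 365 + 30 | 479 |

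The cohort 2 rows apply to patients who start ofatumumab in the study. Patients already stable at screening have a shorter lead-in.

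**Time before any study vaccine dose, cohort 2 starters**
- 2a: 28/627 = 4.5% to 84/690 = 12.2%.
- 2b: 28/423 = 6.6% to 84/479 = 17.5%.

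**Time within 28 days after a protocol dose.** With doses three weeks apart the two windows overlap and cover 21 + 28 = 49 days; at four weeks they cover 56.
- 1a: 49/599 = 8.2% or 56/606 = 9.2%.
- 2a: 49/627 = 7.8% (shortest), 56/690 = 8.1% (longest).
- 1b: 28/395 = 7.1%.
- 2b: 28/423 = 6.6% to 28/479 = 5.8%.
- 1a with two further boosters and no overlap: 112/606 = 18.5%.

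These are shares of time. They equal shares of events only if onset is uniform over the period, which the documents do not show.

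**Effect of follow-up length.** P(at least one event) = 1 − exp(−rate × time), with assumed rates equal for both brands:

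| Events per patient-year | 1a (599 days) | 1b (395 days) | Gap, points | 28 days |
|---|---|---|---|---|
| 0.25 | 33.6% | 23.7% | 9.9 | 1.9% |
| 0.5 | 55.9% | 41.8% | about 14 | 3.8% |
| 1.0 | 80.6% | 66.1% | 14.5 | 7.4% |

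The gap is the extreme case, with one brand used only in 1a and the other only in 1b. Partial imbalance gives less, and equal use gives none.

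**Mixed-brand patients.** Their share is not stated. At an assumed 5% to 40% of the planned 44 (22 per arm), it would be 0.05 × 44 ≈ 2 to 0.40 × 44 ≈ 18 patients.

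**The case against.** The strongest reply has four parts.

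1. A reader might infer that the SAP treats each patient as having one brand and leaves mixed-brand patients without a column. The documents do not say so. Layouts sit in the table shells cited in SAP 2.2.1, which may add a mixed column or count a patient twice. This stands: what can be said is that the SAP text contains no allocation rule. The shells would not, however, change the event period stated in SAP 2.9.1.

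2. A reader might infer that ofatumumab and background events will show up as brand differences. That goes too far. No test or contrast is planned, protocol 12.7 calls all analyses descriptive, and all patients are meant to receive ofatumumab, so its events enter both columns. A spurious gap needs unequal brand use across groups with different follow-up. SAP 2.1 and 2.9 also have results presented by cohort. If that covers the brand table, the mix of cohorts 1 and 2 is dealt with, and the difference in follow-up between a and b remains.

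3. Treatment-related events get their own summary. This helps little, because that summary is not said to separate vaccine from ofatumumab or to be split by brand.

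4. A post-dose window does not isolate the vaccine. Cohort 2 takes ofatumumab monthly throughout, and protocol section 3 lets cohort 1 start from two weeks after the last dose. This also stands: a window reduces such events but does not remove them.

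**Conclusion.** The point holds, confined to one descriptive safety table. Read as written, the SAP places under a vaccine brand all events from about 395 to 690 days of observation. For cohort 2 patients starting ofatumumab in the study, that includes 4 to 12 weeks before any study dose. An illustrative 28-day window after the protocol doses would cover roughly 6% to 9% of the period.

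The missing allocation rule is a gap in the SAP text that the shells may fill. The gap of 10 to 15 points is a possibility under assumed rates and complete separation of brand use, not a prediction.

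The period lengths assume completers and the intervals in protocol 4.5. The primary analysis and the cohort-level adverse-event tables are untouched.

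**What to change.** In SAP 2.9.1, redefine the brand table as follows.

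- **Events:** those starting on or after an in-study modRNA dose and within a pre-specified window after it. The sponsor chooses and justifies the length.
- **Column:** the brand of that dose, shown by cohort.
- **Denominator:** patients with at least one in-study dose of that brand. Patients with both brands count in each.
- **Overlap:** an event falling in two windows is assigned to the most recent dose.
- **Note to the table:** it is descriptive, and background and ofatumumab events are reduced, not removed.

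In SAP 2.4.1, add booster doses to the vaccine frequency table, since the booster is the study vaccine in 1b and 2b.

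The cost is a few lines of SAP text, one re-programmed table and one extended table. The SAP already uses exact vaccination dates (2.4.1) and already has a dose-anchored cut for COVID-19 infections (2.9.1). Protocol 12.5.1 does not list the brand table, so no protocol commitment changes. The downside is that a window has to be chosen, and events outside it appear only in the cohort tables.

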***Booster vaccination is optional can be performed any time after vacc.2. If a booster vaccination is given, an additional unscheduled visit should be performed 1 month after the booster vaccination in order to assess the immune reaction. If this unscheduled visit would be within 2 weeks of the next scheduled visit, the next scheduled visit can be omitted. This only applies for the first and second booster, there won't be any additional visits for potential following boosters.

Cohort 1b and cohort 2b:

PEP: primary endpoint; Vacc.= vaccination with modRNA vaccine;

Vaccination as part of clinical routine and before the study; required number of vaccinations and interval depends on SmPC of respective modRNA vaccines or local regulations provided e.g. by German health authorities.

First booster vaccination as part of clinical routine according to SmPC of respective vaccine or local regulations, e.g. German health authorities. Additional boosters can be performed any time during the study.

* Screening can be performed any time after completion of the initial vaccination cycle (vacc.2). For cohort 2b, ofatumumab treatment has to be initiated at or after screening but at least 4 weeks before booster vaccination

** Ofatumumab initiation doses can be omitted if patient already receives ofatumumab at the time of screening

*** Additional booster vaccination is optional can be performed any time after the first booster. If a second booster vaccination is given, an unscheduled visit should be performed 1 month after the second booster vaccination in order to assess the immune reaction. If this unscheduled visit would be within 2 weeks of the next scheduled visit, the next scheduled visit can be omitted. This only applies for the second booster, there won't be any additional visits for potential following boosters.

The study consists of 2 periods: run-in period and study period.

The **run-in period** comprises the time from screening to vaccination, including the baseline visit (approx. one week before the first vaccination). Patient eligibility will be determined based on the screening and baseline assessments.

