4.5 Risks and benefits

This study does not interfere with clinical routine treatment of MS patients with ofatumumab or SARS-CoV-2 vaccinations. The only intervention is the blood sampling at specific time-points in the course of this trial.

As blood draw is also regularly performed in the clinical routine, the procedure of additional drawings of blood (venous puncture) within this study for antibody- and T-cell response measurements only bear minimal risk for the patient.

Participation in this study might delay initiation of ofatumumab treatment (for patients in cohort 1) or SARS-CoV-2 vaccination (for patients in cohort 2). Duration of the delay depends on multiple parameters:

- For cohort 1, the delay of ofatumumab initiation depends on a) time between screening and appointment for vaccination (1-12 weeks), b) type of vaccination and resulting interval between vaccination one and two (e.g. 3 weeks for BioNTech/Pfizer or 4 weeks for Moderna) and c) on the physician's discretion on how long to wait between last vaccination and ofatumumab initiation (2-4 weeks). In total, the delay will be a minimum of six weeks.
- For cohort 2, the delay of SARS-CoV-2 vaccination will be 4-12 weeks after screening/ofatumumab initiation depending on the physician's discretion.

The overall risks associated with this study are therefore comparable to those in usual clinical practice. Patients will most likely not have a direct benefit from participating in this study except

receiving information about whether SARS-CoV-2 specific antibodies and T-cells can be detected after vaccination.

The results of this study will, however, contribute to a better understanding of the immune responses to modRNA vaccines (initial vaccination and booster) in ofatumumab treated RMS patients. Findings may also provide guidance for the timing of modRNA vaccines and the start of ofatumumab treatment and inform patients and physicians if risk management might be needed.

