6.3.2 Treatment assignment, randomization

No randomization will be performed in this study. The assignment of a participant to a particular cohort will be coordinated by the sponsor.

Cohort 1: will be RMS patients receiving modRNA vaccine as part of the clinical routine prior to starting ofatumumab treatment (Cohort 1a: patients that receive their first SARS-CoV-2 vaccination within the study and cohort 1b: patients that have already completed their initial vaccination cycle and will receive a booster vaccine within the study)

Cohort 2: will be participants receiving modRNA vaccine as part of clinical routine while already stable on ofatumumab treatment for at least 4 weeks (since the first dose) (Cohort 2a: patients that receive their first SARS-CoV-2 vaccination within the study and cohort 2b: patients that have already completed their initial vaccination cycle and will receive a booster vaccine within the study).

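### COVID-19 infections are planned as crude proportions in pooled cohorts 1 and 2 although time at risk differs by design, and the one post-vaccination row treats the pre-vaccination wait differently in 2a and 2b

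*SAP*

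**What the plan says.** Patients developing COVID-19 are the key safety assessment in the Protocol summary. SAP 2.9.1 presents their absolute and relative frequency and adds: "Rates of COVID-19 infections and the rate of COVID-19 infections starting ≥ 7 days after the 2nd vaccination are displayed". It also lists every infection with all COVID-19 vaccination dates. On the level of display, SAP 2.9 says: "Descriptive statistics are presented within study treatment groups (cohorts 1 and 2"). SAP 2.2.1 allows a split into 1a, 1b, 2a and 2b in selected tables, but the table shells are not among the documents.

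In 1a and 2a the second dose is given in the study. In 1b and 2b it is given beforehand. Protocol section 3, in the notes under the design figure, says: "Screening can be performed any time after completion of the initial vaccination cycle (vacc.2"). Protocol 6.3.2 describes "cohort 2b: patients that have already completed their initial vaccination cycle and will receive a booster vaccine within the study".

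Follow-up after the study vaccination runs to 18 months after dose 2 in 1a/2a. In 1b/2b the later visits are at "3 months, 6 months and 12 months (EOS) after the booster vaccine" (Protocol section 3). SAP 2.9.1 counts adverse events from the first study treatment after consent until 30 days after the last visit. SAP 5.2 sets the start at "the date of 1st vaccination or the date of first ofatumumab at or after screening whichever is earlier". Protocol 4.5 gives the lead-in: "For cohort 2, the delay of SARS-CoV-2 vaccination will be 4-12 weeks after screening/ofatumumab initiation depending on the physician's discretion".

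**The concern.** There are two separate issues.

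First, each cohort column mixes patients followed for about 18 months with patients followed for about 12. In cohort 2 the counting window also opens weeks before vaccination for anyone who starts ofatumumab in the study. A longer window gives a higher percentage infected at the same underlying risk. No rule fixes the a/b mix in either cohort, so the columns can differ with no difference in risk. The study is meant to guide the timing of vaccination relative to ofatumumab (Protocol 4.1), so readers will set the two columns side by side even without a formal comparison.

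Second, the post-vaccination row does not cover the same period in the a and b subcohorts. In 2a it starts 7 days after the study vaccination is complete. In 2b it already includes the wait on ofatumumab before the study booster. Elsewhere the SAP names both anchors, for example in 2.4.1: "2nd resp. booster vaccination and Week 1/Month 1/Month 6/ Month 12 after Vaccination 2 resp. booster vaccination are displayed". SAP 2.9.1 does not.

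**Working it through.** **Inputs**
- Follow-up: 18 months = 548 days after dose 2 (1a/2a); 12 months = 365 days after the booster (1b/2b) (Protocol section 3).
- Tail: 30 days after the last visit (SAP 2.9.1).
- Dose interval: 21-28 days, given only as examples (Protocol 4.5).
- Ofatumumab lead-in for cohort 2 starters: 28-84 days (Protocol 4.5). Inclusion criterion 2 expects most cohort 2 patients to be starters.

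Check of the timing inputs: the stated minimum cohort 1 delay is six weeks, and 1 + 3 + 2 = 6 weeks reproduces it.

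**Step 1: on-treatment window** = lead-in + dose interval + follow-up + 30 days
- 1a: 21 + 548 + 30 = 599 to 28 + 548 + 30 = 606 days
- 2a starters: 28 + 599 = 627 to 84 + 606 = 690 days
- 1b: 365 + 30 = 395 days, opening at the booster as the first study treatment after consent
- 2b starters: 28 + 395 = 423 to 84 + 395 = 479 days

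**Step 2: share of the window excluded by the post-vaccination row, read literally**
- 1a: 28/599 = 4.7% to 35/606 = 5.8%
- 2a starters: 56/627 = 8.9% to 119/690 = 17.2%
- 1b and 2b: 0% (at most about 1.4% if a 2b starter is dosed within 7 days of dose 2)

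In 2b starters, pre-booster time is therefore 28/423 = 6.6% to 84/479 = 17.5% of row time. For 2b patients already on ofatumumab it is at most 7/402 = 1.7%. With a study-booster anchor the excluded share would be 7/395 = 1.8% in 1b and 35/423 = 8.3% to 91/479 = 19.0% in 2b starters.

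**Step 3: effect of unequal time on crude percentages**
The hazards are assumptions; the documents give none. Percentage infected = 1 − exp(−h × days/30.44), with h per month, equal and constant in all subcohorts. A 50:50 a/b mix, a 21-day dose interval in both cohorts and all cohort 2 patients as starters give:

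| h | 1a (599 d) | 1b (395 d) | Cohort 1 | Cohort 2, 28-day wait (627, 423 d) | Cohort 2, 84-day wait (683, 479 d) | Gap (points) |
|---|---|---|---|---|---|---|
| 1% | 17.86 | 12.17 | 15.02 | (18.61 + 12.97)/2 = 15.79 | (20.10 + 14.56)/2 = 17.33 | 0.8 to 2.3 |
| 2% | 32.53 | 22.86 | 27.70 | (33.76 + 24.26)/2 = 29.01 | (36.16 + 27.00)/2 = 31.58 | 1.3 to 3.9 |
| 5% | 62.62 | 47.73 | 55.17 | (64.30 + 50.08)/2 = 57.19 | (67.43 + 54.47)/2 = 60.95 | 2.0 to 5.8 |

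A 28-day dose interval leaves these gaps essentially unchanged.

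**Step 4: unequal mixes, at h = 2%**
- 25% a in cohort 1 and 75% a in cohort 2. Cohort 1 = 0.25 × 32.53 + 0.75 × 22.86 = 25.28. Cohort 2 = 0.75 × 33.76 + 0.25 × 24.26 = 31.39 (28-day wait) or 0.75 × 36.16 + 0.25 × 27.00 = 33.87 (84-day wait). The gap is +6.1 to +8.6 points.
- The reverse mix. Cohort 1 = 0.75 × 32.53 + 0.25 × 22.86 = 30.11. Cohort 2 = 0.25 × 33.76 + 0.75 × 24.26 = 26.64 or 0.25 × 36.16 + 0.75 × 27.00 = 29.29. The gap is −3.5 to −0.8 points.

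The a/b mix can thus enlarge or reverse the gap.

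**The case against.** The strongest defence is that the row already has a sensible meaning: infections at least 7 days after completing the two-dose series. Patients in 1b/2b completed that series before screening, so removing none of their time is correct under that definition. The SAP's vaccination shorthand is also inconsistent. Section 2.4.1 tabulates vaccine types only for first and second vaccination, and 5.2 mentions no booster. Little can be read into one missing word. This stands: a reader might infer that the anchor is a mistake, and the documents do not show that.

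A reader might also infer that the word rate has no meaning here. That goes too far, because the same subsection promises absolute and relative frequencies. What is missing is a time-based measure.

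Replacing the anchor with the study booster would have a cost. Breakthrough infections in two-dose-vaccinated 2b patients on ofatumumab would leave the post-vaccination row, and these are of interest. This stands too and shapes the fix.

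Pooling affects all cohort-level adverse event tables, and the shells may already split this one. Protocol 12.4.4 also has initial and booster patients analysed separately, but as a supportive analysis to the primary endpoint. A split would remove the a/b mixing. It would not remove the extra lead-in in cohort 2.

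Finally, the analysis is descriptive, no formal comparison is planned, and cases can be re-sorted from the listing. That is true for cases. The listing holds infected patients only, so it gives no time at risk for the others.

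**Conclusion.** The point holds as a minor one. Crude COVID-19 percentages by pooled cohort rest on unequal time at risk. In the illustration this alone produces about 0.8-2.3, 1.3-3.9 or 2.0-5.8 points between cohorts at 1%, 2% or 5% per month, even with equal a/b mixes. Equal mixes do not bring the gap to about zero unless cohort 2 patients were already on ofatumumab at screening. The figures assume constant and equal hazards, full follow-up, a 3-4 week dose interval and that all cohort 2 patients are starters; hazards and mixes are not in the documents.

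The second-vaccination anchor is defensible but does not give the a and b subcohorts the same period: the pre-vaccination wait is removed in 2a and kept in 2b. This matters mainly for 2b starters; in 1b the choice of anchor moves only 7 of 395 days.

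**What to change.** In SAP 2.9.1:

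1. Beside the planned percentages, give COVID-19 infections per patient-year at risk for 1a, 1b, 2a and 2b.
2. Keep the existing row and label it as at least 7 days after completion of the two-dose series.
3. Add a row for infections starting at least 7 days after the study vaccination, meaning the second dose in 1a/2a and the study booster in 1b/2b. Pre-booster breakthrough infections in 2b then remain visible in the existing row.

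The cost is one label, one row and one denominator. Vaccination, infection and visit dates are already collected. SAP 2.7.1 already computes patient-years for relapses, though in the efficacy set and with no stated subcohort split, so the COVID-19 denominator has to be built on the safety set. Counts per subcohort will be small, and patient-years do not correct for infection risk that changed over calendar time. If the shells already split this table by subcohort, only the denominator, the label and the added row remain to be done.
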